### **6.3. Other Endpoint(s)**

#### **6.3.1. Safety Endpoints**

The following will be summarized according to [Section 5.2](#), using the safety analysis set defined in [Section 4.2](#).

- Incidence of treatment-emergent SAEs and AEs throughout the study.
- Incidence of AESI.
- Categorical summaries of clinical laboratory abnormalities:
  - ALT/AST abnormalities:
    - Value  $\geq 3$  x ULN;
    - Value  $\geq 5$  x ULN;
    - Value  $\geq 8$  x ULN.
  - Percent reduction from baseline in eGFR  $\geq 40\%$ .
  - Platelet abnormality:
    - Confirmed platelet counts  $< 100,000$ ;

- Confirmed platelet counts <75,000;
- Confirmed platelet counts <50,000.
- Platelet count changes:
  - Percent reduction from baseline in platelet counts  $\geq 30\%$ ;
  - Percent reduction from baseline in platelet counts  $\geq 50\%$ .
- UACR;
- ADA.

*Immunogenicity of vupanorsen will be assessed before, during, and after treatment. A listing of individual plasma ADA results (including ADA positive, negative, and unknown status samples and titers) sorted by treatment group, participant ID, planned visit, and the visit date/time will be reported. The incidence (number) and incidence rate (percent) of ADA positive, negative and unknown participants will be summarized by treatment group and planned visit and for the overall study. The ADA positive (ADA+) participants will be further subcategorized into TEADA if the baseline ADA is negative. The incidence and incidence rate of TEADA will be summarized by treatment group and planned visit and for the overall study.*

- ECG (Section 9.4.5.1. of the protocol);
- Vital signs (BP and pulse rate).

The following will be summarized and (percent) change from baseline will be analyzed according to [Section 5.2](#), using the safety analysis set:

- AST;
- ALT;
- Platelet counts;
- eGFR;
- Hepatic fat fraction;
- UACR.

### **6.3.2. Tertiary/Exploratory Endpoints**

The following will be summarized, along with percent change from baseline at Week 24 analyzed according to [Section 5.2](#), using the FASprimary defined in [Section 4.1](#):

- Total cholesterol;
- HDL-C;

- VLDL-C;
- Lp(a);
- FFA;
- ApoB-48;
- ApoB-100;
- ApoC-III;
- ApoA-I;
- HsCRP.

Plasma concentrations of PF-07285557 at planned visit will be listed using the set of PK/PD analysis set (Section 4.3) respectively. Summary tables of vupanorsen concentration by treatment and planned visit with and without stratification by ADA status will also be provided. Population PK and PK/PD analyses may be explored using the combined data from this study and other clinical studies of vupanorsen and reported in a separate population analysis report.

#### 6.4. Subset Analyses

Subgroup analyses of primary and key secondary endpoints (ie, at Week 24) will be performed, to check the consistency of conclusion of treatment effect within each category of the subgroup. The following subgroups will be analyzed:

- Baseline statin use (2 categories: high, low/moderate);
- Baseline TG level (< median, >=median);
- Baseline non-HDL-C level (<median, >=median);
- ADA status (positive, negative);
- BMI (<median, >=median).

FAS\_primary will be the analysis set of subgroup analyses. An ANCOVA model adjusting for baseline value, treatment (categorical), subgroup (categorical) and interaction term of treatment (categorical) by subgroup (categorical) will be applied. The p-value of the interaction term will also be reported.

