Week	-4 to -1			0	1	2	4	6	8	12	16	20	24	32 or 34	
Month	-1						1		2	3	4	5	6	8	
Visit Window (Days)					±1	±1	±2	±2	±2	±3	±3	±3	±3	±7	
Urinalysis	X			X	X i	X	X	X	X	X	X	X	X	X	X
Urine albumin to creatinine ratio	X			X	X i	X	X	X	X	X	X	X	X	X	X
FSH (women, if applicable)	X														
Pregnancy test m	X			X		X	X	X	X	X	X	X	X	X	X
Plasma PK										X n	X n		X o		X
hsCRP				X									X		X
PT, aPTT, INR				X	X i	X	X	X	X	X	X	X	X	X	X
Anti-vupanorsen antibodies (ADA)				X p						X p	X p	X p	X p	X	X
Banked Biospecimen Samples Prep B1.5 (plasma), B2.5 (serum), M4 (urine) q				X									X o		X
Pfizer Prep D1 Banked Biospecimen(s) q				X											
Contraception check				X	X	X	X	X	X	X	X	X	X	X	X
12-Lead ECG	X												X o		X
MRI-PDF r			X										X o,s		X
Randomization				X											
IRT interaction	X	X		X		X t	X	X t	X	X	X	X			X
Study intervention															
Placebo-injection instruction and training		X													
Q2W u,v				X		X i	X	X	X	X	X	X			
Q4W u				X		X i			X	X	X	X			
Review diary to assess treatment compliance										X	X	X	X		X

Visit Identifier a Abbreviations used in this table may be found in Appendix 14 .	Screening b (Days -28 to -1)			Day 1	Day 8	Day 15	Day 29	Day 43	Day 57	Day 85	Day 113 Interim Analysis Time Point	Day 141	Day 169	Follow-up (+12 weeks after last dose) e,f	Early Termination/ Discontinuation g
	Visit 1 c,d	Visit 2	Visit 3												
Week	-4 to -1			0	1	2	4	6	8	12	16	20	24	32 or 34	
Month	-1						1		2	3	4	5	6	8	
Visit Window (Days)					±1	±1	±2	±2	±2	±3	±3	±3	±3	±7	
Prior and concomitant treatment(s)	X			X	X	X	X	X	X	X	X	X	X	X	X
Serious and nonserious adverse event monitoring	X	X	X	X	X	X	X	X	X	X	X	X	X	X	X

Visit Identifier a Abbreviations used in this table may be found in Appendix 14 .	Screening b (Days -28 to -1)			Day 1	Day 8	Day 15	Day 29	Day 43	Day 57	Day 85	Day 113 Interim Analysis Time Point	Day 141	Day 169	Follow-up (+12 weeks after last dose) e,f	Early Termination/ Discontinuation g
	Visit 1 c,d	Visit 2	Visit 3												
Week	-4 to -1			0	1	2	4	6	8	12	16	20	24	32 or 34	

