**Prior/Concomitant Therapy:**

10. Prior treatment at any time with vupanorsen.
11. Prior treatment with any oligonucleotide (including small interfering ribonucleic acid) within 6 months of Screening or prior treatment with inclisiran within 12 months of Screening.
12. Use of TG lowering medication (eg, Vascepa [icosapent ethyl]), non-prescription dietary supplements (eg, fish oil) or other cholesterol lowering medication (eg, fibric acid derivatives, niacin, PCSK9 inhibitors, bile acid sequestrants, bempedoic acid) 30 days prior to Screening, other than statins and ezetimibe.
13. Use of warfarin or other coumarins, direct thrombin inhibitors, Factor Xa inhibitors, heparins or heparinoids 30 days prior to Screening.

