## **7. DISCONTINUATION OF STUDY INTERVENTION AND PARTICIPANT DISCONTINUATION/WITHDRAWAL**

Due to unforeseen circumstances, all participants may not complete the study as planned. Regardless of study intervention status, participants should continue in the study if willing. Possible discontinuations may include:

1. Discontinuation of study intervention: Participants will discontinue study intervention but continue in the study.
  - a. Temporary discontinuation: If a participant temporarily discontinues study intervention for any reason other than safety, they should resume study intervention at the next scheduled dosing, if possible.
  - b. Definitive discontinuation: If study intervention is permanently discontinued (as requested by the investigator or the participant), the participant will remain in the study to be evaluated during the regular visit schedule (see [Section 7.1.2](#) and [Section 7.2.1](#)). At the time of discontinuing from the study intervention, if possible, an Early Termination/Discontinuation visit should be conducted. See the SoA for

assessments to be collected at the time of discontinuation of study intervention and for any further evaluations that need to be completed.

Whenever possible, restart of study intervention should be encouraged. Even if an Early Termination/Discontinuation visit was completed due to the discontinuation of study intervention, this should not prevent complete study follow-up procedures including restart of randomized treatment. All efforts must be taken to assure that the participant will be seen and assessed by an investigator. Participants fulfilling a study-specific discontinuation criteria should never be restarted on study intervention.

2. Participant discontinuation/withdrawal from the study: Participants will not continue in the study (see [Section 7.2](#)).
  - a. Withdrawal of consent (see [Section 7.2.1](#)).
  - b. Lost to follow-up (see [Section 7.3](#)).

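### The ADA interaction p-value in SAP 6.4 does not test consistency of the placebo-adjusted effect if no placebo participant is ADA-positive, and is weak for that purpose if only a few are

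*SAP*

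**What the plan says.** SAP 6.4 plans subgroup analyses of the Week 24 primary and key secondary endpoints "to check the consistency of conclusion of treatment effect within each category of the subgroup". The five subgroups are baseline statin use, baseline TG, baseline non-HDL-C, "ADA status (positive, negative") and BMI. All are analysed in FAS_primary by the same ANCOVA, with terms for baseline value, treatment, subgroup and treatment by subgroup. The section adds: "The p-value of the interaction term will also be reported".

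SAP 6.4 does not say which samples define ADA status. SAP 6.3.1 uses three categories: "The incidence (number) and incidence rate (percent) of ADA positive, negative and unknown participants will be summarized by treatment group", by visit and for the study overall. SAP 6.3.2 tabulates PK "with and without stratification by ADA status", also without defining that status. In the Schedule of Activities (Protocol 1.3), the row "Anti-vupanorsen antibodies (ADA") shows samples on Day 1, at Weeks 12, 16, 20 and 24, at follow-up and at Early Termination/Discontinuation. Protocol 5.2 excludes "Prior treatment at any time with vupanorsen".

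Protocol 2.2.4.1 reports that in Phase 2a, on preliminary analysis, ADA had no apparent effect on Cmax or AUC but went with higher trough concentrations. Protocol 8.9 makes the relation of immunogenicity to efficacy an optional evaluation. SAP 5.1 plans no formal decision rules.

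**The concern.** The other four subgroups are characteristics that placebo and vupanorsen participants share, so each category should hold a usable number from every arm. ADA status is different. The antibodies are directed at a drug that nobody has had before entry and that the placebo arm never receives. In practice, then, positivity arises mainly after randomisation and mainly on vupanorsen.

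This has two consequences. A contrast of ADA-positive vupanorsen participants with ADA-positive placebo participants is not a randomised comparison. There may also be no such placebo participants, in which case the interaction test is no longer about the difference from placebo. The risk is that a non-significant p-value is reported as evidence that antibodies do not alter the effect when the test had little or no ability to show the most obvious alteration, a loss of effect in all arms alike.

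**Working it through.** **Inputs.** SD 17.5 points for non-HDL-C, 15% discontinuation and a 20-point difference (Protocol 9.2). Arm sizes are from SAP Table 1. Taking 85% as available at Week 24 gives 34 placebo participants and 17, 17, 17, 34, 34, 34 and 34 on vupanorsen (187). All ADA rates below are assumptions.

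**The plan's own figure.** 20 × 0.85 = 17 per arm. Half-width = 1.96 × 17.5 × √(2/17) = 11.76; power for 20 points = 91.5%. Both reproduce.

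**Rank.** Columns: intercept 1 + baseline 1 + arm 7 + ADA 1 + interaction 7 = 17. The ADA column minus the sum of the seven interaction columns is the indicator for ADA-positive placebo participants. If there are none, that combination is zero and the rank is 16. Without the interaction the rank is 10, so the test has 16 − 10 = 6 df instead of 7. The seven ADA-positive contrasts with placebo need a placebo-positive mean and are non-estimable. This holds for any endpoint.

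**What the 6-df test sees.** If ADA positivity shifts the mean by the same amount in every vupanorsen arm, arm plus ADA main effect fits all the occupied cells exactly. The non-centrality is zero and the rejection rate is 5%, whatever the size of the shift.

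**Power of the interaction test** (non-central F, α = 0.05). Equal loss: the effect is −20 in every arm and is wholly removed in ADA-positives. Graded loss: assumed effects by rising monthly dose are −10, −15, −15, −20, −20, −28 and −35, also wholly removed.

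| ADA-positive placebo (of 34) | Equal loss, 10% to 40% ADA-positive on drug | Graded loss, 10% to 40% ADA-positive on drug |
|---|---|---|
| 0 | 5% | 22% to 57% |
| 1 to 3 | about 10%, 15%, 20% | 29% to 74% over the range |
| 17, with 50:50 in every arm | 56% | not needed here |

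The graded case with no placebo positives gives 22%, 39% and 57% at 10%, 20% and 40% ADA-positive on drug.

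**Chance of no placebo positives.** (1 − r)^34 = 71%, 50%, 17% and 3% at placebo rates r of 1%, 2%, 5% and 10%.

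**Precision of an ADA-positive contrast with placebo.** Half-width = 1.96 × 17.5 × √(1/p + 1/v), with p placebo and v vupanorsen positives. p = 3, v = 13.6 (40% of 34) gives 21.9; p = 1, v = 1.7 (10% of 17) gives 43.2. The main comparison has 8.3 (34 v 34) or 10.2 (34 v 17).

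**The replacement.** Within vupanorsen, half-width = 1.96 × 17.5 / √(Σ n q(1 − q)), with q the ADA-positive share. With equal rates of 10%, 20%, 30% and 40% it is 8.4, 6.3, 5.5 and 5.1. With rates of 10, 15, 15, 20, 20, 30 and 40% by rising dose it is 6.1. Power for a 10-point difference at the equal rates is 65%, 88%, 95% and 97%. Reading that difference as a loss of effect assumes that ADA status is unrelated to response on placebo.

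**Contrasts with all 34 placebo participants.** ADA-positive: 11.0 (v = 13.6) to 27.0 (v = 1.7). ADA-negative: 8.5 (v = 30.6) to 12.2 (v = 10.2).

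**The case against.** The strongest objection is that an equal loss in every arm is the case least favourable to the test. Protocol 4.3 expects effects to rise with dose: under 8% probability of a 35% mean reduction at 80 mg Q4W, over 90% at 160 mg Q2W. If antibodies removed a graded effect, the loss would differ by arm and the test would have some power even with no placebo positives. This stands. A reader might infer that the p-value can never show anything; the documents do not support that. The test is blind to the part of the loss common to all arms, not to differences between arms.

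Three other inferences should be resisted:

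- That antibodies abolish the lipid effect. Total loss is only a test case. The Phase 2a remark in Protocol 2.2.4.1 gives it no support, and the association with trough levels complicates any ADA comparison, including the replacement.
- That SAP 6.4 must mean post-baseline status because it omits the word baseline for ADA. BMI in the same list lacks the word too. The better ground is the exclusion of prior vupanorsen.
- That the missing time window and missing rule for unknown status are serious in themselves. SAP 6.3.1 offers a candidate, status for the overall study, though 6.4 does not refer to it. This is missing detail that supports the point but would not carry it.

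It is also fair that ADA incidence is tabulated by arm, so an empty placebo cell would be visible, and that ADA-negative contrasts remain estimable. Even a balanced subgroup reaches only 56% in the equal-loss case, so weak interaction tests are general to this section. These facts limit the harm but do not make the p-value answer its stated question.

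**Conclusion.** The point holds and is minor. If no placebo participant is ADA-positive, the reported p-value does not address consistency of the placebo-adjusted effect: the contrasts it should compare are non-estimable, and a loss equal across arms is rejected at 5%, which is alpha. If 1 to 3 are positive, power for an equal 20-point loss is about 10% to 20% and the ADA-positive contrasts with placebo have half-widths of about 22 to 43 points. In either case a non-significant result should not be read as consistency.

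The rank result needs only an empty placebo-positive cell and applies to all five endpoints. The power and precision figures apply to non-HDL-C only and rest on the planned SD, 15% discontinuation and assumed ADA rates and effects. That placebo positives will be few or absent is an inference; pre-existing or assay positives are possible. The analysis is exploratory, has no decision rule, and leaves the primary analysis unaffected.

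**What to change.** Amend SAP 6.4 as follows.

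- Take ADA status out of the treatment-by-subgroup model and drop its interaction p-value. Leave the other four subgroups unchanged.
- Compare ADA-positive with ADA-negative participants within the vupanorsen arms, by ANCOVA on baseline value, arm and ADA status. Label it descriptive and non-randomised, and note that Phase 2a associated ADA with higher trough concentrations, so exposure may confound it.
- If a contrast with placebo is shown by ADA status, use all placebo participants and give it the same label.
- As supporting wording, define ADA status from samples up to and including Week 24, without the follow-up sample. Include any Early Termination/Discontinuation sample in that period, since Protocol 7 says of that visit that "this should not prevent complete study follow-up procedures including restart of randomized treatment". Report the number of participants of unknown status by arm and leave them out of the comparison.

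The change is to SAP wording only. The cost is that no randomised, placebo-adjusted effect by ADA status is reported. The replacement answers a different question, one ADA difference pooled over arms, so its narrower interval is not like for like with a per-arm contrast against placebo.

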#### 6.5. Baseline and Other Summaries and Analyses

##### 6.5.1. Baseline Summaries

Demographic information including age (years), categorical age, sex, race, ethnicity, weight (kg), BMI (kg/m^2) will be summarized by treatment group.

Baseline characteristics including baseline statin products, statin level (high, low/moderate), ezetimibe products, LDL-C (mg/dL), TG (mg/dL), non-HDL-C (mg/dL), ANGPTL3 (ug/L), ApoB (mg/dL), total cholesterol (mg/dL), VLDL-C (mg/dL), HDL-C (mg/dL), HbA1c (%) will be summarized by treatment group.

Medical history on T2DM, atherosclerosis including prior MI, stroke, revascularization, peripheral artery disease (PAD), etc. will be summarized by treatment group.

### **6.5.2. Study Conduct and Participant Disposition**

Number of subjects screened, randomized, discontinuing treatment and study will be tabulated by treatment group.

### **6.5.3. Study Treatment Exposure**

Extent of exposure by treatment group will be summarized at Week 24 and end of study.

### **6.5.4. Concomitant Medications and Nondrug Treatments**

Subjects with specific concomitant medications will be summarized at baseline, Week 24 and end of study, using the WHO-Drug dictionary.

## **6.6. Safety Summaries and Analyses**

### **6.6.1. Adverse Events**

A 3-tier approach will be used to summarize AEs. Risk difference of each dose group (Table 1) vs placebo will be reported.

Tier 1 AEs are clinically important events that come from a Targeted Medical Event (TME) list or any other important clinical consideration (Section 3.5.1). Point estimates, 95% confidence intervals for the risk difference, and p-values will be reported. P-values and confidence intervals are not adjusted for multiplicity and are used for descriptive purpose only.

Tier 2 AEs are those that are not tier 1 AEs, but are more common adverse events of interest and that occur in a pre-specified minimum number /percentage of subjects in one or more treatment groups. For this study, the pre-specified minimum number is 10%. Only point estimates and 95% confidence intervals for the risk difference will be reported. The 95% confidence intervals are provided to help gauge the precision of the estimates for risk difference.

Tier 3 AEs are those that are neither tier 1 nor tier 2 AEs. They won't be identified and reported separately but will be reported as part of the overall AE summary.

AEs will be displayed in alphabetical order of SOC and PT.

It should be recognized that most studies are not designed to reliably demonstrate a causal relationship between the use of a pharmaceutical product and an adverse event or a group of adverse events. Except for select events in unique situations, studies do not employ formal adjudication procedures for the purpose of event classification. As such,

safety analysis is generally considered as an exploratory analysis and its purpose is to generate hypotheses for further investigation. The 3-tier approach facilitates this exploratory analysis.

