### **8.3.8. Adverse Events of Special Interest**

Injection site reactions are AESI. In case of acute injection site reactions, the Investigator should institute treatment measures deemed medically appropriate such as topical therapy at the injection site. Such events and treatments are to be captured and reported on the appropriate CRF. If an injection site reaction occurs at more than 1 injection site location, each location should be captured as a separate injection site AE. For each injection site AE, an injection site assessment should be conducted and captured on the CRF. A separate injection site assessment should be conducted for each injection location where an injection site reaction occurs. The site should also complete the injection site reaction assessment and all concomitant treatments should be recorded and captured in the CRF, together with the Adverse Event of injection site reactions. AEs should be reported as serious per the criteria in [Section 10.3.2](#).

Additional AESI include increases in ALT/AST, decreases in platelet count, or decreases in eGFR (as described in [Section 7.1.1](#)) that result in a missed dose due to temporary dose interruption or permanent discontinuation.

All AESIs must be reported as an AE or SAE following the procedures described in [Sections 8.3.1](#) through [8.3.4](#). An AESI is to be recorded as an AE or SAE on the CRF. In addition, an AESI that is also an SAE must be reported using the CT SAE Report Form.

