### 9.2. Sample Size Determination

Assuming a common standard deviation of 17.5% (observed in the Month 6 data of the Phase 2a proof-of-concept and dose-ranging study) for the percent change from baseline in non-HDL-C at Week 24 and a treatment discontinuation rate of 15%, 20 participants per arm will correspond to a 95% CI of point estimate  $\pm 11.76\%$  for the difference of treatment effect (versus placebo). These parameters correspond to a power of 91.5% using a 2-sided alpha of 0.05, to detect a difference of -20%, without adjustment for multiple comparison to placebo.

A permutation block schedule will be used in enrollment within each arm, including vupanorsen and matching placebo. If enrollment is stopped for the 160 mg Q2W arm (see [Section 4.1](#)), the corresponding matching placebo enrollment will also be stopped.

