**Table 1. Dosing Plan**

Treatment Arm	Total Monthly Dose	Injection Regimen	Number of Participants
Placebo	0 mg	Single or double injection Q2W or Q4W	40
80 mg Q4W	80 mg	Single injection Q4W	20
60 mg Q2W	120 mg	Single injection Q2W	20
120 mg Q4W	120 mg	Double injection Q4W	20
80 mg Q2W	160 mg	Single injection Q2W	40
160 mg Q4W	160 mg	Double injection Q4W	40
120 mg Q2W	240 mg	Double injection Q2W	40
160 mg Q2W	320 mg	Double injection Q2W	40

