### 3.5.1. Adverse Events

Treatment-emergent AE is defined as any adverse event with an onset date no earlier than the first dose of study medication.

A 3-tier approach will be used to summarize AEs. Different analyses will be performed for different tiers (see [Section 6.6.1](#)).

Tier 1 events: These are prespecified events of clinical importance and are maintained in a list in the product's Safety Review Plan.

The full list is not restricted to the following. As the study is ongoing, the study team will monitor all adverse events on a blinded basis and hence the list might be updated accordingly in the safety review plan.

- Injection site reactions.

Tier 2 events: These are events that are not tier 1 but are “common.” A Medical Dictionary for Regulatory Activities (MedDRA) preferred term (PT) is defined as a Tier 2 event if there are at least 10% in one or more treatment groups.

Tier 3 events: These are events that are neither Tier 1 nor Tier 2 events. For this study, tier 3 events won't be reported separately, but will be included in the overall AE summary tables.

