#### 5.1. Hypotheses and Decision Rules

The null hypothesis for the primary endpoint is:

$H_0$ : There is no difference in mean percent change from baseline in non-HDL-C at Week 24 between vupanorsen and placebo.

The study objective is treatment effect estimation and dose selection and therefore no formal decision rules for inferential purposes are planned. Each vupanorsen treatment group will be compared to the pooled placebo group, ie, placebo-adjusted LS-mean treatment effect for each dose will be reported along with 95% CI and p-value without adjustment for multiple comparisons to placebo.

The Mixed Model Repeated Measurements (MMRM) will be used as the primary statistical method to estimate the difference of treatment effect between each dose of vupanorsen versus placebo at Week 24. Statistical inference including effect size, p-value, 95% CI will be presented for primary and secondary endpoints respectively, with no adjustment for multiplicity.

Although an interim analysis will occur at Week 16, no formal hypothesis testing nor statistical inference will be conducted.

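### Injection-site-reaction risk differences use one placebo group that mixes 6-, 12- and 24-injection schedules, which biases the contrasts for the lowest- and highest-count arms

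*SAP*

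**What the plan says.** SAP 3.5.1 lists "Injection site reactions" as the only named Tier 1 event, while noting that the list may grow in the Safety Review Plan. For Tier 1 events SAP 6.6.1 says "Point estimates, 95% confidence intervals for the risk difference, and p-values will be reported". The contrast is set in the same section: "Risk difference of each dose group (Table 1) vs placebo will be reported". The section adds that "P-values and confidence intervals are not adjusted for multiplicity and are used for descriptive purpose only".

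SAP Table 1 has one placebo row, n = 40, whose regimen is given as "Single or double injection Q2W or Q4W". SAP 5.1 says "Each vupanorsen treatment group will be compared to the pooled placebo group". That sentence concerns LS means. For adverse events, pooling follows from the single placebo row and from the absence of any other comparator.

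Protocol 9.2 describes schedule-matched placebo: "A permutation block schedule will be used in enrollment within each arm, including vupanorsen and matching placebo". The SAP does not use the matching for adverse events. It specifies no stratification by schedule, no per-injection rate and no adjustment for injection count; SAP 6.5.3 only summarises extent of exposure by group.

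**The concern.** An injection site reaction needs an injection, so a participant with 24 injections has more chances of at least one reaction than a participant with 6. In this design injection count rises with monthly dose: 6 at 80 mg, 12 at 120 and 160 mg, 24 at 240 and 320 mg. Setting each arm against one placebo group with an intermediate average count therefore puts part of the count effect into the estimate, and that part is ordered by dose.

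The trial is meant to support dose selection, and Protocol 4.3 says injection site reactions will be assessed in a larger sample than before. Protocol 2.3.1 reports that such reactions were dose dependent with unconjugated antisense oligonucleotides. A reader who expects a dose-response could take an artefact of injection count as confirmation, or could read the lowest dose as better tolerated than placebo.

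**Working it through.** The plan states no rate, precision or power for injection site reactions, so there is no figure of its own to reproduce on this point.

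**Scheduled injections.** SoA footnote e places follow-up 12 weeks after the last dose, at Week 32 (Q4W) or Week 34 (Q2W). The last doses are therefore at Weeks 20 and 22, which gives 6 Q4W occasions (Weeks 0 to 20) and 12 Q2W occasions (Weeks 0 to 22). Multiplying by 1 or 2 injections per occasion (Table 1):

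- 80 mg Q4W: 6 × 1 = 6 (20 participants)
- 60 mg Q2W and 80 mg Q2W: 12 × 1 = 12; 120 mg Q4W and 160 mg Q4W: 6 × 2 = 12 (20 + 40 + 20 + 40 = 120 participants)
- 120 mg Q2W and 160 mg Q2W: 12 × 2 = 24 (80 participants)

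**Placebo mix.** The documents do not give the split of the 40 placebo participants. If it is proportional to arm size (assumption), about 3.6, 21.8 and 14.5 have 6, 12 and 24 injections. The mean is (20×6 + 120×12 + 80×24)/220 = 3480/220 = 15.8. With an equal split per arm it is 14.6. If 160 mg Q2W and its matching placebo stop at a quarter of plan, it is 14.5.

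**Direction.** Let r(k) be the risk of at least one reaction after k injections with no drug effect. The pooled placebo risk π is a weighted average of r(6), r(12) and r(24). If r rises with k, then r(6) − π < 0 and r(24) − π > 0 for any split that mixes schedules. The sign for 12 injections depends on the split.

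**Size.** Assume a per-injection risk p that is the same on drug and placebo, independent across injections, and a proportional split. Then r(k) = 1 − (1 − p)^k, and the null risk difference is r(k) − π. At p = 2%, r(6) = 11.4%, r(12) = 21.5%, r(24) = 38.4% and π = (20×11.4 + 120×21.5 + 80×38.4)/220 = 26.7%. The approximate 95% half-width is 1.96 × √[r(1−r)/n + π(1−π)/40].

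| p | π | 6 injections (n = 20): bias, half-width | 12 injections (n = 40): bias, half-width | 24 injections (n = 40): bias, half-width |
|---|---|---|---|---|
| 0.5% | 7.6% | -4.6, ±11.1 | -1.7, ±11.0 | +3.8, ±12.8 |
| 1% | 14.5% | -8.7, ±15.0 | -3.2, ±14.7 | +6.9, ±16.8 |
| 2% | 26.7% | -15.3, ±19.6 | -5.2, ±18.7 | +11.7, ±20.4 |

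Entries after π are percentage points. The two 12-injection arms with n = 20 have the same bias and wider intervals. With an equal split per arm at 2%, the biases are -13.5, -3.4 and +13.5.

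**Illustration with a real drug effect.** Take 3% per injection on drug and 2% on placebo, with the proportional split. For 80 mg Q4W, risk on drug is 1 − 0.97^6 = 16.7%. That is +5.3 points against 6-injection placebo (11.4%) but about -10 against the pool (26.7%), a reversed sign. For a 24-injection arm, 1 − 0.97^24 = 51.9%: +13.4 against matched placebo and +25.1 against the pool.

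**Precision of matched-only comparisons.** Each active arm has one schedule, so a difference stratified by schedule reduces to that arm against its matched placebo cell. At p = 2% the half-width for 80 mg Q4W goes from ±19.6 to ±35.5 points, and for a 24-injection arm from ±20.4 to ±29.2.

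**The case against.** A reader might infer that the pooled placebo spoils the regimen comparison the trial was built for. The documents do not support that. Protocol 4.3 sets that comparison as Q2W versus Q4W at 120 mg and at 160 mg monthly, and all four of those arms have 12 injections. The common placebo also cancels in any difference between active arms. What is affected is the level of each arm against placebo, mainly in three of the seven arms.

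Injection count is also part of the regimen. Syringes hold 60 or 80 mg, so 120 or 160 mg at one time means two injections. The proportion of participants with a reaction on a regimen is a legitimate measure of burden, which a per-injection rate alone would hide. This stands, and is a reason to keep the planned risk difference. It does not rescue the contrast, because pooled placebo is neither a no-injection control nor a same-schedule control.

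The sizes are assumed throughout. At 2% per injection, about 27% of placebo participants would have a reaction, which nothing in the documents supports. With a lower background rate the bias shrinks towards zero. This also stands.

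Finally, the output is labelled descriptive, no decision rule uses it, and Protocol 9.4.5 already plans injection site reactions by treatment group, and by visit where appropriate. So no error rate or formal decision is at risk. But the problem lies in the point estimate, which a descriptive label does not correct.

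**Conclusion.** The point holds as a limited one. The arm-versus-placebo risk difference for injection site reactions is biased downward for 80 mg Q4W and upward for 120 mg and 160 mg Q2W, provided only that placebo risk rises with injection count and that placebo mixes schedules. The four 12-injection arms are less affected.

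The size of about -5 to -15, -2 to -5 and +4 to +12 points for 6, 12 and 24 injections rests on an assumed per-injection risk of 0.5% to 2%, independence across injections, and a proportional placebo split, none of which the documents give. Over that range the bias stays inside the 95% half-width of each contrast. It would be hard to tell from noise in one arm, but its ordering across arms could still look like a dose-response. This is a cheap improvement to a descriptive table and does not affect the efficacy results.

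**What to change.** In SAP 6.6.1:

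1. Keep the participant-level risk difference as a descriptive measure of regimen burden, and label the comparator as a mixed-schedule placebo group.
2. Add a table of injection site reactions per injection received, by arm, with placebo also shown by injection schedule (6, 12, 24).
3. Add an arm-versus-placebo contrast from a count or binomial model with injections received as offset or denominator, and a robust or overdispersed variance for repeated reactions within a participant. State that the output is descriptive.

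A Mantel-Haenszel difference stratified by schedule is not a useful alternative: it collapses to one matched cell per arm, with about 4 placebo participants for 80 mg Q4W.

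The data are already collected. When reactions occur at more than one location, Protocol 8.3.8 says "each location should be captured as a separate injection site AE", and Protocol 6.1.1 and 6.4 put dosing on the CRF. The cost is SAP wording and one extra table. The model assumes a constant per-injection rate. Injections received can also depend on earlier reactions, because Protocol 7.1.2 ends dosing after a severe one; the table should say so.
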